4. STUDY POPULATION

4.1 Population (base)

There is a considerable variability in host-specific factors in the targeted population of this study resulting in a heterogeneous population. Reducing the heterogeneity of the population or stratification for all key variables [28] will result in an inadequately powered study due to a lack of sufficient numbers of eligible subjects. However, due to participation of 13 centre's we are able to reduce variability in patients by narrowing the inclusion criteria, (i.e. exclusion of the group *other patients* (non-hematological malignancies and solid organ transplant recipient)) compared to the study conducted by Herbrecht et al [16]. In previously conducted randomized controlled trials, stratification was performed for risk of infection and antifungal prophylaxis [17]. As diagnosing invasive fungal disease is difficult, the EORTC/MSG, defined three levels of probability of invasive fungal disease: possible, probable or proven invasive fungal disease. These definitions will be used in this study at baseline and again at the end of treatment.

In the Netherlands each year 100 patients are classified as possible, 70 patients as probable and 30 as proven IA. Most of these patients are treated in University Medical Centres, but larger peripheral centres also treat these patients. Due to competing studies from the pharmaceutical industry a part of these potentially eligible subjects will not be included. Due to the more strict in- and exclusion criteria, and refusal to consent, the number of subjects included in these studies will be relatively small. However, some of the eligible study participants will not participate as they refuse informed consent. If these two combined count for half of the patients that are potentially eligible to participate in this study, the number of study participants left to participate in this trial will be sufficient, as by virtue of the trial design of this study proposal, very few patients are expected to drop out.

4.2 Inclusion criteria

- 1) are at least 18 years of age
- 2) have received chemotherapy for haematological malignancies or have received a hematopoietic stem cell transplant
- 3) proven, probable or possible invasive fungal disease according to the EORTC/MSG criteria
- 4) treatment with voriconazole

4.3 Exclusion criteria

- 1) allergic to voriconazole or its excipients
- 2) age below 18 years

4.4 Sample size calculation

In a previous randomized trial with voriconazole in a dosage according to product leaflet with similar inclusion criteria the response was: complete in 20%, partial in 30%, stable in 10% and failure in 40% [16]. As TDM will probably result in the largest benefit in patient with low voriconazole trough levels, who are not responding, or in patients with high trough levels, who stopped because of side effects, the sample size calculation of this study is based on the reduction of patients failing on voriconazole therapy. For control patients (treated without TDM) a failure rate of 40% is expected [16], while for patients during the experimental TDM episode, a failure of 20% is expected. Under the most unfavourable assumption that the intra cluster correlation coefficient equals the intra period correlation coefficient varying between 0.002 and 0.02, and knowing that at least 12 centres are participating in this study, each cluster must include 16 patients to obtain a power of about 80% with an unreliability of 5% (two-sided) to detect a clinically relevant improvement of 20% of reduction of patients failing on voriconazole at day 28 of treatment compared to control. This means that in total 192 patients are necessary for performing this study. To compensate for loss during follow-up in total 200 patients will be included. Loss during follow-up is defined as patients not willing to continue participation because of personal reasons. Patient stopping because of voriconazole adverse effects are noted as "failure".

5. TREATMENT OF SUBJECTS

5.1 Investigational product/treatment

The intervention (TDM) consists of taking serum samples at day three of treatment, measuring the voriconazole serum levels and adjusting the dosage to reach the therapeutic window. Dosing of voriconazole will be done during the control period according to the product brochure.

Voriconazole is registered for treatment of invasive Aspergillosis. Product leaflet is added as attachment,

5.2 Use of co-intervention (if applicable)

Not applicable

5.3 Escape medication (if applicable)

Not applicable.

6. INVESTIGATIONAL MEDICINAL PRODUCT

6.1 Name and description of investigational medicinal product

Vfend® (voriconazole); ampul 200mg; tablet 200mg; suspension 40mg/ml.

6.2 Summary of findings from non-clinical studies

See attached 1B brochure

6.3 Summary of findings from clinical studies

See attached 1B brochure

6.4 Summary of known and potential risks and benefits

See attached 1B brochure

6.5 Description and justification of route of administration and dosage

See attached 1B brochure for route of administration for both groups and for starting dosage in both group (6mg/kg IV bid; 400mg PO bid) and for maintenance dose in control group (4mg/kg IV bid; 200mg PO bid)

As in daily practice serum concentration levels are measured for toxicity or therapeutic failure, the attending physician may request a concentration level. This request is subjected to a protocol: toxicity (rise in liver enzymes > 5 times upper level of normal values, after starting voriconazole), failure (no clinical, microbiological or radiological response after 7 days of treatment with voriconazole).

6.6 Dosages, dosage modifications and method of administration

Dosage modification in intervention group:

In a previous randomised trial with voriconazole in a dosage according to product brochure the response to therapy was: complete in 20%, partial in 30%, stable infection in 10% and progressive infection (failure) in 40% [16]. As too high (occurring in 10-25% of cases) or too low (25-60%) voriconazole serum concentrations can potentially be avoided by TDM guided dosing the percentage of subtherapeutic and toxic voriconazole concentrations can be reduced from 25-60% and 10-25% respectively to < 10%. As TDM is most likely to benefit patients with low voriconazole trough levels who are not responding or in patients with high trough levels who stopped because of side effects a reduction of failure from 40% to 20% can be anticipated to occur with TDM. During the TDM episode, the voriconazole dosage will be adjusted to achieve trough serum concentrations in a predefined window of 2-5 mg/L. Voriconazole serum concentrations after the 5th dosage (IV 6mg/kg for the first 24 hours followed by 4mg/kg bid, PO 400mg for the first 24 hours followed by 200mg bid) will be measured in all patients during

treatment with voriconazole during the TDM period. Two blood samples will be drawn, one immediately before the dose ($t=0$) and one 2h after the dosage ($t=2$) when administered orally or 1h after the end of infusion when administered intravenously. If the serum trough level is < 2.0 mg/L the dosage will be increased. If the serum trough level is > 5 mg/L the dosage will be reduced. Dosage adjustment will be performed according to a standard algorithm. Three days after dosage adjustment a control sample series is drawn, followed by the same dose adjustment algorithm. After reaching the therapeutic window trough levels, surveillance samples will be drawn twice a week while the patient is in the hospital. For outpatient treatment trough levels will be drawn at regular visits of the patients to the outpatient clinic (about once every two weeks). Since outpatients are clinically more stable, fluctuations are expected to be less frequent, moreover patients are often put on voriconazole during hospital stay and have a stable level when leaving the hospital.

6.7 Preparation and labelling of Investigational Medicinal Product

Not applicable

6.8 Drug accountability

Not applicable

7. METHODS

7.1 Study parameters/endpoints

7.1.1 Main study parameter/endpoint

Defining the primary endpoints in a heterogeneous study population is difficult. A combined endpoint (global response) consisting of clinical, microbiological and radiological response to therapy has been previously used previously and is well accepted in clinical trials investigating the efficacy of antifungal agents [17, 29-31]. The global response, consisting of a combination of clinical, microbiological and radiological responses on day 28 of treatment, will be categorized as one of the following four possible outcomes:

- 1) Complete Response: resolution of all clinical signs and symptoms and more than 90 percent of the IA related lesions that were visible on radiographic studies at baseline;
- 2) Partial Response: Clinical improvement and greater than 50 percent improvement in radiological findings present at baseline;
- 3) Stable: No change from baseline, or an improvement of less than 50 percent in radiological findings;
- 4) Failure: Worsening disease and death

The primary endpoint is a reduction in risk of failure on voriconazole therapy. This failure is based on the categorized global response.

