Rationale: Patients with haematological malignancies and chemotherapy induced prolonged neutropenia are at risk for severe bacterial and fungal infections. These opportunistic infections can result in prolonged hospital stay, increases costs and greater mortality. Voriconazole has now been recommended as the first line agent for invasive pulmonary aspergillosis (IA). Retrospective observational studies of voriconazole serum concentration suggest that serum concentration correlate with toxicity and clinical response. These observations were however made in small series of patients and data were collected retrospectively. These inherent methodological flaws make it impossible to draw definite conclusions about the effect of voriconazole serum concentration monitoring on the outcome of IA, and therefore considered insufficient proof to recommend voriconazole concentration determination in blood as standard of care. The impact that so-called serum concentration guided dosing of voriconazole will have on treatment success can only be evaluated through a prospective randomized clinical trial.

Objective: The objective of this study proposal is to determine whether pharmacologic optimization of voriconazole by means of therapeutic drug monitoring (TDM) results in improved patient outcomes (efficacy and safety) and is more cost-effective compared to the current standard of care.

Study design: we designed a prospective stratified cluster randomized cross-over trial of therapeutic drug monitoring in patients with haematological disease who have developed IA. The order of periods (TDM or standard of care, each 12 months) will be randomized per centre.

Study population: Patients with haematological malignancies and possible, probable or proven IA according to EORTC criteria.

Intervention (if applicable): In the intervention group the voriconazole dosage will be adjusted to achieve trough blood concentrations in a predefined window of 2-5 mg/L. In the control group voriconazole will be dosed according to product leaflet.

Main study parameters/endpoints: The primary clinical endpoint will be a global response consisting of a combined endpoint of toxicity and response to therapy (clinical, microbiologic and radiologic responses) 28 days after starting treatment with voriconazole. A sample size of n=192 is needed to detect a 20% absolute reduction in the number of

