As too low (< 2 mg/L) or too high (> 5 mg/L) voriconazole serum concentrations are observed in 25-60% and 10-25% of patients respectively TDM has the potential to improve treatment outcome. Optimizing antifungal therapy through concentration based dosing of voriconazole fits within the theme of pharmacotherapy as it is likely to optimize efficacy of treatment in the individual patient. This approach could be cost-effective through the prevention of toxicity and treatment failure that requires the use of more expensive antifungal agents for salvage therapy. At present, no randomized trials have addressed the question whether the use of TDM improves the outcome of voriconazole therapy. We hypothesize that therapeutic failure, now estimated around 40% can be reduced by half - i.e., to 20% using TDM. Failure is defined clinically. In a previous randomised trial with voriconazole in a dosage according to product leaflet the response to therapy was: complete in 20%, partial in 30%, stable infection in 10% and progressive infection (failure) in 40% [16]. As TDM is most likely to benefit patients with low voriconazole trough levels who are not responding or in patients with high trough levels who stopped because of side effects a reduction of failure from 40% to 20% can be anticipated to occur with TDM.

At present, there is a paucity of well-conducted studies on the added value and cost-effectiveness of TDM in general [26,27], and no data exists on the costs-effectiveness of TDM in patients with IA in particular. The costs of TDM in the present study proposal are estimated to be between €315 and €790 per patient per treatment episode, depending on the time elapsed until an adequate voriconazole serum level is reached. The costs of voriconazole may be higher in the early phase of therapy compared to the standard dosing scheme, due to an increase in dosage. However, in the latter phase of therapy these costs could be reduced by a switch from intravenous to oral therapy, or a shorter duration of treatment as a consequence of a better response to treatment. Furthermore, an increase in

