7.1.2 Secondary study parameters/endpoints (if applicable)

- 1) mortality at day 28 and week 12 of therapy due to fungal infection, overall mortality at 28 days and 12 weeks.
- 2) resolution of neutropenic fever, defined as percentage of patients with a oral temperature of $<38\text{ }^{\circ}\text{C}$ at day 7 of voriconazole treatment [17]; time (in days) to resolve fever is also noted.
- 3) percentage of voriconazole serum concentrations within the targeted window of 2-5mg/L during therapy based on repeated measurements in time.
- 4) percentage switched to salvage therapy (i.e. amphotericin B or one of its lipid or liposomal formulations; or echinocandin (e.g., caspofungin/anidulafungin) or other triazole (e.g., posaconazole); or measured concentration level in control arm during treatment for toxicity or failure)

- 5) side effects (visual disturbance and liver enzymes) Side effects leading to drug discontinuation.
- 6) time (in days) of to global response as defined under the primary endpoint definition after the start of voriconazole
- 7) The evaluation of cost-effectiveness (hospital and societal per perspective) of voriconazole TDM in patients with invasive aspergillosis will be an integral part of this project.

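### The primary endpoint, failure at day 28, is defined both with and without toxicity, and it is unclear which version the 40% and 20% planning rates describe

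*Protocol*

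**What the plan says.** Four places in the protocol bear on what counts as failure.

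- **Section 7.1.1** sets out the components: "The global response, consisting of a combination of clinical, microbiological and radiological responses on day 28 of treatment". Four categories follow (complete, partial, stable, failure), none with a toxicity term. The last is "Failure: Worsening disease and death". The section then ties the primary endpoint to these categories: "This failure is based on the categorized global response".
- **The Summary** describes the primary endpoint as "a global response consisting of a combined endpoint of toxicity and response to therapy", assessed 28 days after voriconazole is started.
- **Section 4.4**, next to its definition of loss to follow-up, gives a further rule: "Patient stopping because of voriconazole adverse effects are noted as" failure.
- **Section 7.1.2** lists "Side effects leading to drug discontinuation" within secondary endpoint 5, apart from the primary endpoint.

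On the planning rates, section 1 reports the earlier trial's results as "stable infection in 10% and progressive infection (failure) in 40% [16", and section 6.6 repeats this. Section 4.4 gives the same 40% simply as failure. All three sections argue the fall to 20% partly from patients with high trough levels who stopped because of side effects.

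**The concern.** These are conflicting rules for the one outcome on which the trial is powered. They are not a detail left for a later document. An analysis plan could elaborate any one of them, but it would have to override at least one protocol section to do so.

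The patients affected are those in whom TDM might act by preventing toxicity. Under 7.1.1, someone who stopped for an adverse effect but improved by day 28 does not count against the allocated strategy. Under 4.4, the same person does. The expert panel is asked to review the primary endpoint at the end of the study (section 3) without one rule to apply. The treatment effect being estimated, the expected event rates and the power all depend on which rule is used.

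**Working it through.** **1. One patient under each rule.** Take a patient with clinical improvement and more than 50% radiological improvement at day 28, who stopped voriconazole for an adverse effect.

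| Place | Classification |
|---|---|
| 7.1.1 | Partial response, not a failure |
| 4.4 | Failure |
| Summary | Toxicity counts towards the endpoint; no rule for combining it with response |
| 7.1.2 | Event counted under secondary endpoint 5 |

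**2. The protocol's own sample size.** Inputs from 4.4: 40% v 20% failure, two-sided 5%, power about 80%, at least 12 centres, 16 patients per centre (so 8 per centre and period), and an intracluster correlation of up to 0.02.

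- Two proportions, pooled variance under the null: n = [1.96·√(2·0.3·0.7) + 0.842·√(0.4·0.6 + 0.2·0.8)]² / 0.2² = 81.2, so 82 per arm and 164 in total.
- Design effect, taking the between-period correlation as zero: 1 + (8 − 1)·0.02 = 1.14. The protocol does not print its formula; this choice is the reconstruction that gives its figure.
- 164 × 1.14 = 187. Divided by 12 this is 15.6, so 16 per centre and **192** in total, as stated.
- Power at 192: effective n per arm = 96 / 1.14 = 84.2, giving **81%**.

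**3. What the definition does to rates and power.** The protocol gives no rate of stopping for adverse effects, so every rate below is an assumption. N is 192 and the design effect 1.14 throughout.

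(a) *40% and 20% are disease failure only; a share d of the remaining control patients stop, and TDM halves that share.* Control = 0.40 + 0.60d; TDM = 0.20 + 0.80·d/2.

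| d | Control | TDM | Power |
|---|---|---|---|
| 5% | 43% | 22% | 84% |
| 10% | 46% | 24% | 86% |
| 20% | 52% | 28% | 90% |
| 25% | 55% | 30% | 91% |

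Patients who change class with the definition: control 96 × 0.60 × d = 2.9 to 14.4; TDM 96 × 0.80 × d/2 = 1.9 to 9.6. That is about 3 to 14 and 2 to 10 of 96.

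(b) *As (a), but with the same stopping share in both arms.* TDM = 0.20 + 0.80d.

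| d | Control | TDM | Power |
|---|---|---|---|
| 5% | 43% | 24% | 75% |
| 10% | 46% | 28% | 68% |
| 20% | 52% | 36% | 55% |

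(c) *40% and 20% already include toxicity stops, and the response-only version of 7.1.1 is analysed, with the halving kept.*

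| Control | TDM | Power |
|---|---|---|
| 35% | 17.5% | 74% |
| 30% | 15% | 65% |

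**The case against.** The best defence has three parts. First, failure on voriconazole therapy could be read as naturally including having to stop the drug. Second, the sentence in 4.4 could be only a rule separating loss to follow-up from outcome. Third, an analysis plan that is not shown may settle the derivation.

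None of this removes the conflict. The sentence in 7.1.1 that ties failure to the four categories closes off the first reading. The rule in 4.4, whatever its purpose, assigns an outcome that 7.1.1 does not, and the Summary brings toxicity in independently. An analysis plan could choose a version, but the protocol would still contradict itself.

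Other parts of the defence do stand, and they limit what a reader may infer:

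- **That counting toxicity stops costs power.** Not in general. If TDM halves the stops, power rises from 81% to 84–91%. It falls only under other assumptions, such as (b) or (c).
- **That the 40% belongs to the response-only version.** Sections 1 and 6.6 do call it progressive infection, but 4.4 says only failure, and the expected benefit is argued partly from toxicity stops. The documents leave open what the 40% covers.
- **That avoiding toxicity is half of the expected benefit.** The protocol does not say so. It gives low concentrations in 25–60% of patients and high ones in 10–25%.
- **That 7.1.1 requires both worsening and death.** A literal conjunction does not fit sections 1 and 6.6, where progression alone is failure. The wording is an editorial slip.
- **That the definition is open to choice once results are known.** Section 3 has a panel unaware of allocation review both the primary endpoint and secondary endpoint 5. Both components are thus assessed blind, which limits this worry, although the rule for combining them remains unsettled.

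**Conclusion.** The inconsistency is real and concerns the primary endpoint. Sections 7.1.1 and 4.4 classify the same patient differently, the Summary sides with including toxicity, and the protocol contains nothing to settle the matter. It is also unclear which version the 40% and 20% describe.

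The stated sample size is arithmetically sound for the rates given. The effect of the definition on power cannot be fixed from the documents because no toxicity-stop rate is given. Over the assumed scenarios, power at 192 runs from about 55% to about 91%, and the direction depends on whether TDM reduces such stops and on what the 40% already contains. The documents therefore do not support a conclusion that the trial is underpowered. They support the narrower one that its power is not determined until the endpoint is.

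**What to change.** Before the panel's end-of-study review:

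1. Reconcile the Summary, 4.4 and 7.1.1 to one definition of failure that says explicitly whether stopping for an adverse effect overrides a good day-28 response.
2. Report the version not chosen as a secondary or sensitivity analysis.
3. State in 4.4 which version the 40% and 20% refer to. If they refer to the version not chosen, restate the expected rates and the power.
4. As an editorial correction, change the failure category in 7.1.1 to worsening disease or death.

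The cost is amendment wording and one additional analysis, with no new procedures. The restated power may be higher or lower than the 81% that the present inputs give.

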Voriconazole is the first line treatment of IA among patients with haematological malignancies and hematopoietic stem cell transplant recipients according to recent international guidelines [43] as reported in a large randomised trial [16]. Recent observational studies suggest that voriconazole serum concentrations of at least 1 to 2.0 mg/L are associated with improved clinical outcome [18, 19, 42]. This clinical finding is supported by the in-vitro susceptibility of *Aspergillus fumigatus* to voriconazole [20]. On the other hand high trough concentrations exceeding 5 mg/L are associated with toxicity, mainly neurological and hepatotoxicity [40, 42,46]. It has also been shown that the inter-individual variation of voriconazole plasma levels is significant due to hereditary factors that influence the rate of clearance of the drug. Consequently, the guidelines for the treatment of IA published recently by the Infectious Diseases Society of America (IDSA) recommend monitoring of voriconazole concentration levels and adjusting dosage accordingly as an option for patients not responding to the standard weight-based dosing of voriconazole. This may be caused by sub-therapeutic serum concentrations or treatment discontinuation due to side effects that might be caused by toxic serum concentrations. Monitoring of serum

concentrations and adjusting the dose will be an alternative to switching to other antifungal agents such as a lipid formulation of amphotericin B, caspofungin or posaconazole [43].

Furthermore, voriconazole treatment is relatively expensive itself (€400/day for parenteral treatment) and suboptimal use can be expected to result in therapeutic failure, and additional costs incurred by the need for more expensive salvage antifungal therapy and prolonged hospital stay. We hypothesize that dosing of voriconazole based on serum concentration (so-called therapeutic drug monitoring) will result in improved clinical outcome of patients with IA, by reducing the risk of therapeutic failure and toxicity and that this will be cost-effective [39, 41, 43]. A multi-center randomized controlled clinical trial was designed to test this hypothesis [21, 22, 41].

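### The primary endpoint is named as failure on voriconazole but scored from day-28 status alone, so a patient switched for lack of response who is then stable or better counts as a non-failure

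*Protocol*

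**What the plan says.** Protocol 7.1.1 names the endpoint: "The primary endpoint is a reduction in risk of failure on voriconazole therapy". The next sentence ties failure to the global response on day 28, which has four categories: complete, partial, stable and failure. The last reads "4) Failure: Worsening disease and death". No category mentions which antifungal the patient is taking, or whether it was changed.

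Other sections bear on how a change of drug should count:

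- Section 4.4 sizes the trial on patients failing on voriconazole and records a stop for voriconazole adverse effects as failure. It has no matching rule for a stop or switch for lack of response.
- Section 7.1.2, item 4, lists "percentage switched to salvage therapy" as a secondary endpoint and names the salvage drug classes.
- Section 5.3 marks escape medication as not applicable.
- Section 1 speaks of treatment failure that leads to salvage with costlier drugs, and expects TDM to save money by preventing such switches.
- Section 6.5 allows a concentration to be requested for failure, there meaning no response after 7 days of voriconazole.

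**The concern.** The endpoint's name and its scoring rule can disagree about the same patient. Take someone with no response after a week who is changed to another drug and has stable or improved disease on day 28. In plain terms voriconazole failed; under the 7.1.1 categories the patient is stable, a partial response or a complete response, all of which are non-failures. Had the same patient stopped because of side effects, section 4.4 would call it failure. The scoring of a drug change thus depends on its reason, in a trial whose treatment allocation is not blinded.

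At stake is what the primary result means. Rescue by another drug lowers the observed failure rate wherever it happens. If it happens equally in both arms, the absolute difference shrinks in proportion. If it happens more in control periods, the difference shrinks further, and a null result could reflect effective salvage as much as an ineffective TDM strategy. The cost-effectiveness ratio in the Summary, expressed per therapeutic failure prevented, uses the same notion of failure.

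**Working it through.** **Inputs from section 4.4.** "For control patients (treated without TDM) a failure rate of 40% is expected", "while for patients during the experimental TDM episode, a failure of 20% is expected". Two-sided 5%, power about 80%, 12 centres of 16 patients (192 in total, 8 per centre and period), correlation 0.002 to 0.02.

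**Input not in the documents (assumption).** r is the share of would-be failures who are switched before day 28 and then score as non-failures. The values tried are 10% and 20%, equal or unequal between arms. It is also assumed that the 40% and 20% are rates before any rescue; the protocol does not say whether they are.

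**Step 1, reproduce the plan's figure.** Patients per arm without clustering, with p̄ = 0.30:

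n = [1.96·√(2·0.30·0.70) + 0.842·√(0.40·0.60 + 0.20·0.80)]² / 0.20² = 81.2, so 82 per arm and 164 in total.

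Design effect, giving no credit for correlation between the two periods of a centre: 1 + (8 − 1)·0.02 = 1.14. Then 164 × 1.14 = 187, or 15.6 per centre, rounded up to 16; 16 × 12 = 192. The stated figure is reproduced.

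**Step 2, power at 192.** Effective patients per arm m are 96/1.14 = 84.2 at correlation 0.02 and 96/1.014 = 94.7 at 0.002.

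Power = Φ{ [|p₁ − p₂|·√m − 1.96·√(2p̄(1 − p̄))] / √(p₁(1 − p₁) + p₂(1 − p₂)) }

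For 40% vs 20% and m = 84.2: (0.20 × 9.177 − 1.270)/0.632 = 0.89, so 81.4%. For m = 94.7: 85.7%.

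**Step 3, apply the written scoring rule.** The observed rates become 0.40·(1 − r control) and 0.20·(1 − r TDM).

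| Rescued, control / TDM | Observed failure | Difference (points) | Power, correlation 0.02 to 0.002 |
|---|---|---|---|
| 0 / 0 | 40% vs 20% | 20 | 81–86% |
| 10% / 10% | 36% vs 18% | 18 | 75–80% |
| 20% / 20% | 32% vs 16% | 16 | 68–74% |
| 20% / 10% | 32% vs 18% | 14 | 56–61% |
| 10% / 20% | 36% vs 16% | 20 | 85–89% |

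The last row reverses the expected direction and shows how far the result depends on it: with more rescue under TDM, power is not lost. Equal rescue in both arms does cost power.

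**Step 4, set the rules side by side.** Stop for adverse effects: failure (4.4). Switch for lack of response, then stable or better on day 28: non-failure (7.1.1), though counted in 7.1.2 item 4. That item cannot recover the number of switches by arm as it stands, because in the control arm it also counts a concentration measured for toxicity or failure.

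**The case against.** Day-28 status whatever drug is being taken is a legitimate endpoint for comparing two treatment strategies, with salvage reported and costed separately. It rests on a blinded panel's assessment, whereas a switch is decided by clinicians who know the allocation. Scoring switches as failures brings that open-label decision into the primary endpoint and could favour TDM. This stands as a real cost of the fix. It does not remove the defect: the protocol does not describe its endpoint as a strategy endpoint, names it as failure on voriconazole, and already accepts an open-label decision for adverse-effect stops.

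A reader might infer that rescued patients are credited mainly to the control arm. The documents do not establish that. Section 1 says that monitoring "concentrations and adjusting the dose will be an alternative to switching to other antifungal agents", but this follows a guideline option for patients not responding to standard dosing and does not describe a difference between arms. Section 6.5 gives control patients without a response after 7 days a route to a measured level. The expectation in section 1 that TDM prevents switches is a cost hypothesis.

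A reader might also infer that the planning rates measure something else, or that power must fall to about half. Whether the cited trial's 40% already includes patients on salvage cannot be seen; if it does, the control rate would not fall as in the table. Larger rescue shares have no source: the roughly 50% response in section 1 is a general rate for voriconazole and lipid amphotericin B, not a rate after voriconazole has failed.

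The panel could score worsening before a switch as failure, but no rule tells it to. Two supporting points are weak: the entry in 5.3 may be only a template answer, and added (rather than substituted) drugs are simply not mentioned, while 7.1.3 does record medication used and refers to a CRF that is not shown.

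**Conclusion.** The point holds in this form: the name of the primary endpoint and its scoring rule conflict for patients switched for lack of response, and the scoring is inconsistent with the adverse-effect rule in 4.4. This is the definition of the primary endpoint, which the protocol itself fixes, so it is not detail left for an analysis plan.

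The sample size of 192 is not in dispute. The effect on power is illustrative: modest at 10% equal rescue, material at 20%, and largest if rescue is commoner in control. It rests on an assumed rescue share, on planning rates that exclude rescued patients, and, for the unequal case, on an inferred direction. Patients affected are non-failures rather than successes, since stable disease is among the outcomes they may reach.

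**What to change.** In 7.1.1, state the adverse-effect rule now found only in 4.4, and beside it add a scoring rule: a change to, or addition of, another mould-active antifungal before day 28 for lack of response is scored as failure on voriconazole. The blinded panel should adjudicate this from the dated record and the stated reason, in both arms alike, without sight of information that reveals the allocation. A change for another reason is not failure under this rule.

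Report day-28 status regardless of drug as a prespecified sensitivity analysis, and show both results, because open-label switching could favour TDM. Report drug switches by arm separately from concentrations measured in control.

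Reconcile 4.4, 5.3, 7.1.1 and 7.1.2. This is a scoring rule only; it sets no rule for when or how treatment is switched.

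The cost is protocol wording, panel instructions and, if the CRF does not already hold them, the start date, drug and reason for each other antifungal. At 192 patients the power stays at 81–86% if 40% and 20% are the rates under this definition. The sponsor should confirm that, because some switched patients might otherwise have been graded stable.
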